##### **Exclusion criteria:**

- (1) Hepatic disease, e.g. twice the normal levels of liver enzymes;
- (2) Kidney disease, e.g. twice the normal level of serum creatinine;
- (3) Bupivacaine sensitivity or known allergy;
- (4) Women who are pregnant or breastfeeding;
- (5) Anticoagulants considered to be a contraindication for TAP blocks;
- (6) Surgeries with high port sites;
- (7) Weight <70 kg.

### **C. Withdrawal Criteria**

Patients will be free to withdraw from study at any time. Patients will also be removed from study at any time for adverse events, or deemed necessary for patient safety.

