## Specific Aims

Pain management after major abdominal surgery remains challenging. The best-accepted traditional analgesic approach is continuous epidural analgesia. However, epidural analgesia is rapidly being replaced by transversus abdominis plane (TAP) blocks. TAP infiltration is an alternative to epidural blocks for providing postoperative analgesia to the anterior abdominal wall. TAP infiltrations are relatively easy to perform, generally safe, and can be performed in patients who are anti-coagulated. TAP infiltration can be performed as a single injection, or a catheter can be inserted for continuous local anesthetic infusion.

Single shot plain bupivacaine is often used for TAP blocks, but plain bupivacaine provides <24 hours of analgesia. Catheters provide analgesia for longer, but they are difficult to position properly and difficult to maintain in the proper anatomical location. An alternative to TAP catheters is infiltration of liposomal bupivacaine which, in other sites, lasts up to three days. But whether liposomal bupivacaine is preferable to plain bupivacaine for TAP blocks remains controversial, with available studies being sparse and inconclusive.

We therefore proposed to compare single-shot TAP infiltration with liposomal bupivacaine, plain bupivacaine, and placebo on length of anesthetic effect determined by the opioid consumption. We will evaluate the following specific aims, all of which will be assessed over 72 hours, or the duration of hospitalization if shorter:

**Primary Aim 1:** To assess the relative effects of TAP blocks with liposomal bupivacaine, plain bupivacaine and placebo on cumulative opioid consumption in first 24 hours with TAP blocks.

**Primary Aim 2:** To assess the relative effects of TAP blocks with liposomal bupivacaine, plain bupivacaine and placebo on cumulative opioid consumption in 24 to 48 hours with TAP blocks.

**Secondary Aim 1:** To assess the relative effects of TAP blocks with liposomal bupivacaine, plain bupivacaine and placebo on the duration of abdominal wall analgesia (determined by pinprick and cold).

**Secondary Aim 2:** To assess the relative effects of TAP blocks with liposomal bupivacaine, plain bupivacaine and placebo on pain after surgery in first 72 hours.

**Secondary Aim 3:** To assess the relative effects of TAP blocks with liposomal bupivacaine, plain bupivacaine and placebo on cumulative opioid consumption 48 to 72 hours.

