### **D. Protocol**

After eligibility is confirmed, patients will receive complete information about the study both verbally and in writing. Informed consent will be obtained from the patients prior to randomization and study-specific procedures.

Randomization will be based on computer-generated codes and use random-sized blocks. Allocations will be concealed until the morning of surgery where they will be provided by a web-based system. Randomization will be stratified by study site and chronic opioid use, defined by opioid use for more than 30 consecutive days within three preoperative months, at a daily dose of 15 mg or more of morphine or equivalent. Randomization will also be stratified according to anticipated type of surgery (open vs. laparoscopic-assisted). Clinicians doing the blocks will not be involved in data collection and all the evaluators will be blinded to group allocations.

All blocks will be performed preoperatively or after induction of anesthesia by attending anesthesiologists or regional anesthesia fellows who are experienced in TAP blocks. Premedication will be administered at the discretion of the attending anesthesiologist and standard monitors will be used. Patients will be given 1 g oral acetaminophen an hour before surgery, and an additional 500 mg every 6 hours for 72 hours after surgery starting with oral intake.

Patients will be randomly assigned to: 1) 4-quadrant TAP block with liposomal bupivacaine; 2) 4-quadrant TAP block with plain bupivacaine; or, 3) placebo (normal saline). An in-plane ultrasound will be guide TAP blocks. Two subcostal injections will be applied by placing the probe midline and then moving lateral along the subcostal margin identifying area between the rectus abdominis sheath and the transversus abdominis muscle. The lateral two TAP block injections will be applied in the midaxillary line between

the thoracic cage and iliac crest between external oblique and transversus abdominis muscles. Once the target area is positioned, the following injections will be given, based on randomization:

**Liposomal bupivacaine.** 40 ml of plain bupivacaine 0.25% will be mixed with 20 ml liposomal bupivacaine and 20 ml of saline. 20 ml of the mix will be injected at each location of the 4-quadrant TAP block.

**Plain bupivacaine group.** 50 ml of plain bupivacaine 0.5% will be combined with 30 ml of normal saline making a total of 80 ml. 20 ml will be injected at each location of the 4-quadrant TAP block.

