### ***Primary Outcome 1***

Opioid requirements will be measured as the total amount of opioids (converted to morphine sulfate equivalents) used during the first 24 postoperative hours after surgery. Use of PCA and discontinuation will be recorded.

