### ***Primary Outcome 2***

Opioid consumption will be measured as morphine equivalents between 24-48 hours.

To evaluate TAP blocks with liposomal bupivacaine, plain bupivacaine, and placebo on opioid consumption in 24 to 48 hours. Use of PCA and discontinuation will be recorded.

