### ***Tertiary Outcome 1***

A composite of opioid-related side effect after surgery will be recorded for 72 hours. Components of the composite include nausea, vomiting, ileus, constipation, pruritus, itching, urinary retention, use of antiemetics or naloxone or antihistamines.

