### ***Tertiary Outcome 3***

Total cost of hospital care and specific care costs will be estimated from data in the electronic medical records database. Data obtained from electronic medical records will include: operation time, surgery type, intraoperative opioid consumption, postoperative opioid consumption in PACU and in ward, breakthrough pain medication requirements, pain scores in PACU and ward, requirement of oxygen in PACU and ward, pruritus, requirement of antihistaminic medications, requirement of naloxone, itching, ambulation time, flatus, ileus, bowel movements (first time documented), constipation, length of stay and any side effects or complications.

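### Removing patients from the study for adverse events may end outcome collection for opioid-related reasons, although the only study treatment is a single block already given

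*Combined protocol and SAP*

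**What the plan says.** Section C (Withdrawal Criteria) first lets patients withdraw when they wish, then adds a second route that does not depend on the patient's request: "Patients will also be removed from study at any time for adverse events, or deemed necessary for patient safety". It sets no severity threshold and does not say whether data collection continues after removal.

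The Specific Aims describe the intervention; the trial will "compare single-shot TAP infiltration with liposomal bupivacaine, plain bupivacaine, and placebo". Section D (Protocol) gives its timing: "All blocks will be performed preoperatively or after induction of anesthesia". The two primary outcomes are measured later. The first is total opioid "used during the first 24 postoperative hours after surgery". For the second: "Opioid consumption will be measured as morphine equivalents between 24-48 hours".

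Tertiary Outcome 1 sets out what the protocol regards as opioid-related side effects: "Components of the composite include nausea, vomiting, ileus, constipation, pruritus, itching, urinary retention, use of antiemetics or naloxone or antihistamines".

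Section F (Data Analysis) specifies linear regression on log morphine equivalents for the primary outcomes. It names no analysis population, no missing-data method and no sensitivity analysis for removed patients. Section G (Sample Size Considerations) raises 67 per group to 79 for the interim analyses only. The one kind of shortened follow-up that the plan addresses is early discharge.

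**The concern.** In a trial with repeated dosing, withdrawal for an adverse event can at least stop further exposure. Here exposure is complete before either primary window opens. For a postoperative event, removal from the study therefore stops no study drug, and on the plain reading it stops follow-up.

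The loss may be informative. Nausea, vomiting, ileus, pruritus, urinary retention and naloxone use are common reasons to record a postoperative adverse event, and the protocol itself ties them to opioids. A patient removed on day 1 for such an event could lose part of the 0-24 h total, the whole 24-48 h outcome and later pain scores, and would have incomplete 72 h side-effect data. If removal is related to opioid use and its frequency differs between arms, a complete-case comparison of geometric means is biased. Because no analysis set is defined, nothing in the plan prevents a complete-case analysis.

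**Working it through.** **Sequence of events.** Block before surgery or after induction (Section D); then surgery; then primary windows 0-24 h and 24-48 h (Primary Outcomes 1 and 2); side effects recorded to 72 h (Tertiary Outcome 1). Removal for any postoperative event falls after the last study dose.

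**Inputs from Section G.** CV 0.85; ratio of geometric means 0.60; 67 per group fixed, 79 maximum; 90% power; overall alpha 0.05.
- Log-scale SD: σ = √ln(1 + 0.85²) = 0.737.
- Log effect: δ = |ln 0.60| = 0.511.

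**The plan's own figure.** n = 2(z₁₋α/₂ + z₀.₉₀)²σ²/δ². The per-comparison alpha is not stated. With an assumed 0.05/6 (three pairs, two periods), n = 2 × (2.638 + 1.282)² × 0.5438/0.2609 = 64.0, so 65 per group, or 66 with the noncentral t. That is within two of the stated 67. Removals are not part of this figure. If they occurred, 79 evaluable per group would need 79/(1 − d) randomised: 84, 88 or 99 at d = 5%, 10% or 20%.

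**Assumptions for the illustrations.** The documents give no removal rate and no link between removal and opioid use, so every rate and correlation below is assumed. Removed patients are left out of the analysis.

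*Moderate link.* Removal propensity correlates ρ with log opioid use. If a proportion p is removed, the mean of those retained shifts by −ρσφ(z₁₋ₚ)/(1 − p). The factor φ(z₁₋ₚ)/(1 − p) is 0.109 at 5%, 0.195 at 10% and 0.274 at 15%. Observed ratio = 0.60 × exp(shift in active − shift in placebo).

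| Removed, placebo vs active | ρ = 0.3 | ρ = 0.5 |
|---|---|---|
| 5% vs 5% | 0.60 | 0.60 |
| 10% vs 5% | 0.61 | 0.62 |
| 15% vs 5% | 0.62 | 0.64 |
| 5% vs 10% | 0.59 | 0.58 |

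Example (15% vs 5%, ρ = 0.5): the shifts are −0.101 and −0.040, the difference is 0.061, and 0.60 × e^0.061 = 0.638.

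With a true ratio of 1.00, the 15% vs 5% case is observed as 1.04 to 1.06. At 79 per group, keeping σ = 0.737 and ignoring interim looks, the two-sided 5% error becomes about 6.0% to 7.8%.

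*Extreme link.* Removal takes exactly the highest consumers (ρ = 1), 10% of placebo vs 3% of active.
- Shifts: −0.195 × 0.737 = −0.144 and −0.070 × 0.737 = −0.052. Ratio: 0.60 × e^0.092 = 0.66.
- Truncation also reduces the SDs, to 0.622 and 0.685. Patients remaining: 67 × 0.90 = 60.3 and 67 × 0.97 = 65.0.
- SE = √(0.622²/60.3 + 0.685²/65.0) = 0.117. Log effect |ln 0.658| = 0.419. Power at two-sided 0.025 = Φ(0.419/0.117 − 2.241) ≈ 91%.
- With no removal: SE = 0.737 × √(2/67) = 0.127 and power = Φ(0.511/0.127 − 2.241) ≈ 96%.

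**The case against.** The case on the other side is that the rule is a routine safety sentence, will be used rarely, and does not say that data collection stops. Its strongest support is in the protocol: "A composite of opioid-related side effect after surgery will be recorded for 72 hours", and Section D allows antiemetics for symptoms after surgery. The trial plainly expects ordinary side effects to be treated and counted in patients who stay in. This stands. A reader might infer that everyone with a composite event would be removed, but that would leave the composite almost nothing to count. A patient whose event was recorded before removal could also still count in it.

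A reader might also infer that the rule removes high consumers mainly from placebo and so dilutes the effect. The documents do not support a fixed direction. They give no adverse-event or removal rates by arm, and reactions to the local anaesthetic would fall on the active arms. In the moderate model, equal removal gives no bias and heavier removal on active reverses it.

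Nor is it right that removal achieves nothing. It would end sensory testing, leg-raise scores and the 72 h limits on some co-analgesics, and an event before injection could stop the block. For postoperative events, those ends can be met without stopping outcome collection.

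Finally, a power of about 85% in the extreme case is tempting. It arises only if the mean is shifted while the SD of 0.737 and all 67 patients per arm are kept, which is inconsistent with removing the top consumers. The consistent figure is about 91%.

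What the objection does not supply is any text that continues outcome collection after removal or defines who is analysed.

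**Conclusion.** The point holds in a limited form. The withdrawal rule is an actual instruction. As written it may remove patients from the primary outcomes for reasons related to opioid use, when the treatment can no longer be withdrawn. No analysis set, missing-data rule or dropout allowance offsets this.

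Size and direction cannot be derived from the documents. Under the assumed moderate link the distortion of a true 0.60 is modest, and the 0.66 case is an extreme rather than an expectation. The conclusion rests on reading removal from the study as the end of follow-up, which is the plain reading but is not expressly stated. It should be corrected because the repair is small, but it does not by itself invalidate the design.

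**What to change.** Amend Section C to separate stopping study procedures from stopping follow-up. An adverse event may end study procedures as clinicians judge necessary, but it does not end outcome collection. Opioid use, pain scores and side effects continue to be taken from the medical record to 72 h or discharge. Only withdrawal of consent for data use ends collection. No clinical management rule is proposed.

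Add to Section F that all randomised patients are analysed as randomised, and state how values that cannot be recovered from the record, such as sensory tests and leg-raise scores, will be handled.

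The cost is one sentence in Section C and a short addition to Section F. Tertiary Outcome 3 already draws "postoperative opioid consumption in PACU and in ward" from the electronic record, together with pain scores, several named side effects and a general entry for side effects and complications, so no new data system is needed.

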### **D. Protocol**

After eligibility is confirmed, patients will receive complete information about the study both verbally and in writing. Informed consent will be obtained from the patients prior to randomization and study-specific procedures.

Randomization will be based on computer-generated codes and use random-sized blocks. Allocations will be concealed until the morning of surgery where they will be provided by a web-based system. Randomization will be stratified by study site and chronic opioid use, defined by opioid use for more than 30 consecutive days within three preoperative months, at a daily dose of 15 mg or more of morphine or equivalent. Randomization will also be stratified according to anticipated type of surgery (open vs. laparoscopic-assisted). Clinicians doing the blocks will not be involved in data collection and all the evaluators will be blinded to group allocations.

All blocks will be performed preoperatively or after induction of anesthesia by attending anesthesiologists or regional anesthesia fellows who are experienced in TAP blocks. Premedication will be administered at the discretion of the attending anesthesiologist and standard monitors will be used. Patients will be given 1 g oral acetaminophen an hour before surgery, and an additional 500 mg every 6 hours for 72 hours after surgery starting with oral intake.

Patients will be randomly assigned to: 1) 4-quadrant TAP block with liposomal bupivacaine; 2) 4-quadrant TAP block with plain bupivacaine; or, 3) placebo (normal saline). An in-plane ultrasound will be guide TAP blocks. Two subcostal injections will be applied by placing the probe midline and then moving lateral along the subcostal margin identifying area between the rectus abdominis sheath and the transversus abdominis muscle. The lateral two TAP block injections will be applied in the midaxillary line between

the thoracic cage and iliac crest between external oblique and transversus abdominis muscles. Once the target area is positioned, the following injections will be given, based on randomization:

**Liposomal bupivacaine.** 40 ml of plain bupivacaine 0.25% will be mixed with 20 ml liposomal bupivacaine and 20 ml of saline. 20 ml of the mix will be injected at each location of the 4-quadrant TAP block.

**Plain bupivacaine group.** 50 ml of plain bupivacaine 0.5% will be combined with 30 ml of normal saline making a total of 80 ml. 20 ml will be injected at each location of the 4-quadrant TAP block.

**Placebo group;** patients will receive total of 80 ml of normal saline, injected 20 ml in each of the four-quadrant sites.

General anesthesia will be induced using propofol or etomidate, fentanyl, and rocuronium to facilitate intubation. Anesthesia will be maintained with sevoflurane or isoflurane, along with opioids and muscle relaxants as clinically indicated. However, intraoperative analgesic use will be limited to fentanyl, a short-acting opioid.

Postoperatively, patients will be given intravenous patient-controlled analgesia and nurses will be free to give additional opioid as clinically indicated. Hydromorphone will be the default drug, but fentanyl will be substituted if necessary. Clinicians blinded to trial drug will adjust analgesic management as necessary in an effort to keep verbal response pain scores (details below) <4 points on a 0-10 scale, with 10 being worst pain. When patients no longer need PCA, they will be switched to as-needed hydromorphone or fentanyl.

A single dose of dexamethasone (4-8 mg) will be given to all patients for PONV prophylaxis, and inhaled steroids will be permitted as necessary to treat reactive airway disease. The use of non-steroidal anti-inflammatory drugs and gabapentinoids will be allowed as part of the ERAS approach (enhanced recovery after surgery) according to hospital's clinical practice. Other opioid-sparing medications such as ketamine and lidocaine patches will not be permitted through the initial 72 postoperative hours. Vital

signs and patient activity will be continuously monitored and recorded with a wireless monitor (ViSi mobile, Sotera Wireless, San Diego, CA). Monitoring will be started about 30 minutes after arrival in the postanesthesia care unit and continued for 72 hours while patients remained hospitalized. Clinicians will be blinded to continuous monitoring data; clinical decisions therefore will be guided by routine intermittent vital signs which were typically obtained at 4-hour intervals.

Patients will be allowed to receive prophylactic anti-emetic (first choice ondansetron) intraoperatively based on the risk assessment for nausea and vomiting. Postoperative anti-emetics for symptomatic treatment will also be allowed; again ondansetron will be the first choice.

### **E. Measurements**

Demographic data to be obtained includes height (cm), weight (kg), age (yr), sex, (ASA) physical status, self-declared ethnicity, and the specific type of procedure will be recorded. Patients will be questioned about tobacco and alcohol use, and about illegal drug use. They will also be asked about their medical history including pulmonary disease, kidney disease, diabetes mellitus, neurological disease, chronic pain conditions, previous surgery or stent placement, and medications. Available preoperative laboratory tests and medication list will be recorded. Preoperative pain scores and opioid use will be recorded. Patients excluded for any reason including technical considerations or contraindications will be recorded.

All the procedures for the ultrasound guided TAP blocks will be recorded to the ultrasound and two blinded independent adjudicators will evaluate the success of the blocks. Blocks will be accepted as successful if 3 out of 4 locations were done correctly according to adjudicators.

### ***Primary Outcome 1***

Opioid requirements will be measured as the total amount of opioids (converted to morphine sulfate equivalents) used during the first 24 postoperative hours after surgery. Use of PCA and discontinuation will be recorded.

### ***Primary Outcome 2***

Opioid consumption will be measured as morphine equivalents between 24-48 hours.

To evaluate TAP blocks with liposomal bupivacaine, plain bupivacaine, and placebo on opioid consumption in 24 to 48 hours. Use of PCA and discontinuation will be recorded.

### ***Secondary Outcome 1***

The duration of the local anesthetic effect (determined by pinprick and cold) will be evaluated in all four quadrants. The evaluation will be made in eight locations, three in each side and two in midline. The first will be below the subcostal margin at midclavicular line, the second will be on the midclavicular line between the thoracic cage and iliac crest level of umbilicus, the third will be below umbilicus on the same line. The same sites will be evaluated on the contralateral side. There will be two more locations on midline. The first will be midway between umbilicus and xiphoid, and the second will be midway between umbilicus and midpoint of a line drawn between iliac crests.

Cold tests will be performed by using ice contained in a clean nitrile glove, first applied to the patient's forearm where they will be asked to describe how it feels to confirm ice cold. Then the same ice-filled glove will be applied to the same 8 points on the abdomen described above, asking the patient to confirm "yes" when they feel cold equivalent or greater to that on their forearm. Pinprick will be evaluated by calibrated force of 256 mN and a flat contact area of 0.2 mm in diameter using a stimulator (PinPrick Stimulator Set, MRC Systems, Heidelberg, Germany).

The initial measurement will be in the preanesthesia care unit, prior to block administration. The first postsurgical evaluation will be performed within 5-30 minutes of the patient arriving in the post-anesthetic care unit (PACU) or the intensive care unit (ICU), whichever is applicable. Two further assessments will be performed in PACU/ICU/regular

nursing floor at one hour intervals. Subsequently, assessments will be performed at 2 hourly intervals (x3) then at 12 hours postop (defined as patient leaving the OR), 18 hours postop, 24 hours postop, 30, 36 hours postop, 48 hours postop, 60 hours postop, 72 hours postop (when patients are not sleeping). Testing will continue until abdominal wall sensation returns or 72 hours have elapsed since surgery. We will consider sensation recovered when patients feel both ice and pinprick in at least 6 of the 8 designated test locations. If the TAP block did not initially cover all eight locations, sensation will be considered recovered when patients sense ice and pinprick at  $\geq 75\%$  of the covered points (i.e., 5/7, 5/6, 4/5, 3/4, 3/3, etc.). Two sequential evaluations will be needed to be negative and first negative time will be accepted as the return of sensation.

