## **Secondary Aims**

### **Secondary Aim 1:**

To assess the duration of the local analgesia (determined by pinprick and cold) in all four quadrants with liposomal bupivacaine, plain bupivacaine, and placebo after major abdominal surgery.

Hypothesis. Abdominal wall analgesia from four-quadrant TAP blocks with single-shot liposomal bupivacaine lasts longer after major abdominal surgery than the same blocks with plain bupivacaine or placebo. Our major outcome will be time from end of the block until abdominal wall sensation with both ice and pinprick recovers in at least six of eight designated locations. Two sequential evaluations will be needed to be negative and first negative time point will be accepted as the return of sensation.

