#### **B. Setting and Population**

##### **Inclusion criteria:**

- (1) Written informed consent;
- (2) 18-85 years old;
- (3) ASA Physical Status 1-3;
- (4) Scheduled for elective open or laparoscopic-assisted abdominal surgery;
- (5) Anticipated hospitalization of at least three nights;
- (6) Expected requirement for parenteral opioids for at least 72 hours for postoperative pain;
- (7) Able to use IV PCA systems.

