## **Secondary Outcomes.**

*Time to return of sensation.* We will compare the 3 randomized groups on the time to detection of return of sensation (see above; i.e., when patients feels both ice and pinprick in at least 6 of the 8 designated test locations, or  $\geq 75\%$  of the covered points if the TAP block did not initially cover all eight locations) using a time-to event Kaplan-Meier analysis and log-rank test, and comparing patients on the estimated median time to return of sensation. If all patients do have return of sensation (as expected), the analysis will be equivalent to a Wilcoxon rank sum test, and so this test and the corresponding Hodges-Lehman estimator of median difference (CI) will be reported as a sensitivity analysis. The significance criterion for each of the 3 comparisons will be  $0.05/3 = 0.0167$  to control the type I error at 0.05 for the primary outcome.

*Pain score.* We will compare the 3 randomized groups on mean pain score over the first 72 hours using a linear mixed effects model in which we adjust for within-subject

correlation assuming an autoregressive correlation structure (or unstructured or other, whichever fits best; but making sure to also account for the differences in timing between the measurements) with fixed effects of treatment and categorical time. While we will assess the treatment-by-time interaction, main results will be reported collapsing over time regardless of a significant interaction.

*Opioid consumption 48-72 hours.* This will be analyzed using linear regression as with the primary outcomes.

[figure not shown]
Type I error will be controlled at 0.05 for secondary outcomes by using a significance criterion of  $0.05/3=0.017$  for each outcome.

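### A return of sensation first seen at a patient's last test cannot be confirmed and has no coding rule; with discharge before 72 hours this can overstate block duration, mainly in the longer-acting arm

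*Combined protocol and SAP*

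**What the plan says.** Secondary Outcome 1 (section 3.E, Measurements) schedules the late sensory tests at 12, 18, 24, 30 and 36 hours after leaving the operating room, then "48 hours postop, 60 hours postop, 72 hours postop (when patients are not sleeping". It sets the end of testing: "Testing will continue until abdominal wall sensation returns or 72 hours have elapsed since surgery". It also sets the event rule: "Two sequential evaluations will be needed to be negative and first negative time will be accepted as the return of sensation". Secondary Aim 1 repeats that rule: "Two sequential evaluations will be needed to be negative and first negative time point will be accepted as the return of sensation". A negative test here means that sensation is back.

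Specific Aims says of the aims: "all of which will be assessed over 72 hours, or the duration of hospitalization if shorter". Eligibility asks for "Anticipated hospitalization of at least three nights".

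Secondary Outcomes (section 3.F) plans Kaplan-Meier, log-rank tests and a comparison of medians. It then adds a Wilcoxon test with a Hodges-Lehmann estimate, introduced by "If all patients do have return of sensation (as expected". No section says how to code a patient whose only recovered test is the last one.

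**The concern.** The confirmation rule needs one more test than the schedule provides at its end. A patient first found recovered at 72 hours, or at the last test before discharge, has an observed recovery that the definition does not accept. Kaplan-Meier would then carry that patient as censored at the moment of recovery, although the method assumes that censoring is unrelated to recovery.

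The loss would not fall evenly. Specific Aims puts plain bupivacaine below 24 hours and describes "infiltration of liposomal bupivacaine which, in other sites, lasts up to three days". If that holds for this block, the liposomal arm has far more recoveries near the end of follow-up.

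The size of the duration estimate matters as well as the test. Medians are to be compared, and the Economic Analysis divides the cost difference by the mean difference in time to return of sensation. With no rule in the plan, the coding would be chosen after the data exist.

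**Working it through.** The plan gives no sample size, median or censoring rate for this outcome, so there is no stated figure to reproduce. Hours below are counted from leaving the operating room, as in the test schedule.

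**1. What can be confirmed.** The 36- and 60-hour tests fall 24 and 48 hours after the 12-hour test, so all three share one clock time. A patient leaving the operating room at 14:00 has all three at 02:00. For any exit between 11:00 and 18:00 they fall between 23:00 and 06:00.

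| Situation | Late tests available (h) | Latest first recovery that can be confirmed (h) |
|---|---|---|
| All tests done, stays 72 h | 36, 48, 60, 72 | 60 |
| All tests done, leaves between 60 and 72 h | 36, 48, 60 | 48 |
| 36 and 60 h missed asleep, stays 72 h | 30, 48, 72 | 48 |
| 36 and 60 h missed asleep, leaves between 48 and 72 h | 30, 48 | 30 |

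**2. All tests done, everyone stays 72 hours.** Return is dated at the first of the two tests, so only recoveries first seen at 72 hours are lost. A simulation on the schedule assumed lognormal durations with a coefficient of variation of 0.5 and censored unconfirmed recoveries at the last test.

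- Liposomal median 48 h: proportion still blocked at 48 h, S(48), is 0.50 with or without the rule.
- Median 60 h: S(60) is 0.50 either way; S(72) is 0.50 under the written rule and 0.35 if the last test counts.
- Median 66 h: S(72) is 0.58 against 0.43; the estimated median is not reached against 72 h.

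**3. Some patients discharged early, no tests missed.** Same model, with 20% or 40% discharged uniformly between 48 and 72 hours.

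| Assumed liposomal median | Quantity | No rule | Rule, 20% early | Rule, 40% early |
|---|---|---|---|---|
| 48 h | S(48) | 0.50 | 0.524 | 0.546 |
| 60 h | S(60) | 0.50 | 0.535 | 0.574 |

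The mean restricted to 72 hours rises by about 0.5 to 1.5 h in the liposomal arm and 0.3 to 0.6 h in the plain arm (median 24 h). The share of patients with a single unconfirmed recovery, from no early discharge to 40%, is:

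- plain, median 24 h: 1.6% to 4.4%
- liposomal, median 36 h: 6.9% to 11.3%
- liposomal, median 48 h: 12.3% to 15.6%
- liposomal, median 60 h: 15.0% to 16.3%

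**4. Early discharge and missed night tests together.** Assume a liposomal median of 44 h, log SD 0.35, exit between 09:00 and 18:00, tests between 23:00 and 06:00 missed, and 20% leaving at 11:00 on day 3. The true value is S(48) = 1 − Φ(ln(48/44)/0.35) = 1 − Φ(0.249) = 0.40. The written rule gives 0.47, and counting the last test returns 0.40. The plain arm is almost unaffected.

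**5. The log-rank test.** Rejection rate at 0.0167 with 67 per arm and no missed tests:

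| Medians (h) | Early discharge | Written rule | Last test counts |
|---|---|---|---|
| 24 vs 36 | none | 0.99 | 0.99 |
| 24 vs 36 | 30% | 0.97 | 0.99 |
| 48 vs 60 | none | 0.50 | 0.51 |
| 48 vs 60 | 30% | 0.45 | 0.49 |

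**The case against.** The other side has good points, and most of them stand.

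- **Early discharge is limited by design.** Patients must be expected to stay three nights and to need parenteral opioids for at least 72 hours. Some will still leave before hour 72, since a third night can end in a morning discharge, but nothing supports a large share.
- **Sleep assumptions drive the larger figures.** If every exit falls between 11:00 and 18:00 and all night tests are lost, the 36- and 60-hour tests vanish for everyone; exits from 09:00 bring the loss to about 78%. The plan's remark about sleeping patients might also allow a test on waking.
- **Kaplan-Meier tolerates censoring.** It does, when censoring is uninformative. That covers the full-stay case up to 60 hours, but not a patient censored because recovery was seen at the last test before going home.
- **The stop rule need not be a contradiction.** Return can be read as confirmed return. That is a fair reading, and one word would settle it.
- **The Wilcoxon analysis is conditional and only a sensitivity analysis.** True, so losing it leaves the main test intact.
- **Accepting one test late but two tests early makes the definition depend on time.** This is a real cost and the reason for a sensitivity analysis. The simulations contain no false recovered tests, so they cannot show its size.

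**Conclusion.** The concern holds in a conditional form. The text leaves a last-test recovery unconfirmable and uncoded, and read literally it is not an event. With full attendance and a 72-hour stay, the damage is confined to the 72-hour step, and the median is lost only if about half an arm is still blocked at 60 hours. With discharge before 72 hours, duration can be overstated, mainly in the longer-acting arm, and missed night tests enlarge this. S(48) of 0.47 against 0.40 is one illustration under stated assumptions, not an estimate for this trial.

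A reader might infer that the liposomal block duration will be overstated or cannot be estimated, or that a third or more of that arm's recoveries will be lost. The documents do not support this: such figures need heavy early discharge or wholesale loss of night tests, and the plan gives neither rate. A reader might also infer that the bias is wholly one-sided or threatens the significance test. The plain arm shifts a little too in some scenarios, and the log-rank decision barely moves in the settings checked, which did not include missed night tests. That the liposomal arm is the more affected is an inference from the expected durations. This is a secondary outcome; the correction is worth making because it is cheap and must be settled before the data are seen.

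**What to change.** In Secondary Aim 1, Secondary Outcome 1 and Secondary Outcomes (section 3.F), state that a first recovered test at the patient's last available assessment, whether at 72 hours or the last before discharge, counts as return of sensation at that time. Require a second recovered test only when a later test exists. Report the number of unconfirmed events by arm, with a sensitivity analysis that censors them or treats them as interval-censored.

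Reword the stop rule so that testing continues until return of sensation is confirmed or 72 hours have elapsed. Remove from section 3.F the expectation that all patients will have an event.

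The cost is protocol and SAP wording; no test is added beyond the confirmation already required. A few unconfirmed recoveries may be false, and the sensitivity analysis will show how much they matter.
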